9.5.2 Schedule of Procedures/Assessments

9.5.2.1 Schedule of Procedures/Assessments

[Table 4](#) presents the schedule of procedures/assessments for the study.

Table 4 Schedule of Procedures/Assessments in Study APD356-G000-401

Phase	Pre-randomization	Randomization																		
Period	Screening	Treatment																	F/U	
Visit	1	2 ^a	3	4	5	6	7	8	9	10	11	12	13	14	15	16	17	EOT	EOS	Unsch ^b
Month ^c	Days -30 to -1	Day 1	3	6	9	12	15	18	21	24	28	32	36	40	44	48	52	56		
Assessment (revised per Amendment 01)																				
Informed consent	X																			
Demography	X																			
Medical history	X																			
Cardiovascular history	X																			
Diabetes history	X																			
Tobacco history/use		X				X				X			X			X		X		
Inclusion/ exclusion criteria	X	X																		
Physical examination	X					X				X			X			X		X		
Vital signs	X	X	X	X		X		X		X	X	X	X	X	X	X	X	X	X	X
Height	X																			
Weight	X	X	X	X	X	X	X	X	X	X	X	X	X	X	X	X	X	X		
Waist/hip circumference	X	X				X				X			X			X		X		
Echocardiogram ^d	X			X		X		X		X			X			X				
12-lead ECG		X				X				X			X			X		X		
Hematology laboratory tests ^e	X			X		X				X			X			X		X		
Chemistry laboratory tests ^{e,f}	X			X		X				X			X			X		X	X	

Table 4 Schedule of Procedures/Assessments in Study APD356-G000-401

Phase	Pre-randomization	Randomization																	F/U	
Period	Screening	Treatment																		
Visit	1	2 ^a	3	4	5	6	7	8	9	10	11	12	13	14	15	16	17	EOT	EOS	Unsch ^b
Month ^c	Days -30 to -1	Day 1	3	6	9	12	15	18	21	24	28	32	36	40	44	48	52	56		
Assessment (revised per Amendment 01)																				
Serum cystatin C/serum creatinine ^{f,g}		X				X				X			X			X		X	X	
Urinalysis incl. ACR ^f	X					X				X			X			X		X	X	
PGx sampling (where applicable)		X																		
HbA _{1c} sampling ^f	X	X	X	X		X		X		X		X	X	X	X	X	X	X	X	X
Fasting plasma glucose ^f	X	X		X		X				X			X			X		X	X	X
Fasting insulin level ^f	X	X		X		X				X			X			X		X	X	
Other biomarker sampling (where applicable)		X		X						X								X		
hsCRP	X					X				X			X			X		X		
Fibrinogen		X				X				X			X			X		X		
Urine drug screen	X																			
Pregnancy test ^h	X	X																		
Diet and exercise counseling	X	X	X	X	X	X	X	X	X	X	X	X	X	X	X	X	X			
Randomization		X																		
IxRS ^e	X	X	X	X	X	X	X	X	X	X	X	X	X	X	X	X	X	X	X	
Prior/concomitant medications ⁱ	X	X	X	X	X	X	X	X	X	X	X	X	X	X	X	X	X	X	X	

Table 4 Schedule of Procedures/Assessments in Study APD356-G000-401

Phase	Pre-randomization	Randomization																		
Period	Screening	Treatment																	F/U	
Visit	1	2 ^a	3	4	5	6	7	8	9	10	11	12	13	14	15	16	17	EOT	EOS	Unsch ^b
Month ^c	Days -30 to -1	Day 1	3	6	9	12	15	18	21	24	28	32	36	40	44	48	52	56		
Assessment (revised per Amendment 01)																				
Study drug dispensing ^e		X	X	X	X	X	X	X	X	X	X	X	X	X	X	X	X	X		
Collect study medication ^e			X	X	X	X	X	X	X	X	X	X	X	X	X	X	X	X	X	
Drug accounting & compliance ^e			X	X	X	X	X	X	X	X	X	X	X	X	X	X	X	X	X	
AE monitoring ⁱ	<----->																			
MACE/MACE+ reporting ⁱ	<----->																			

(revised per Amendment 01)

Notes: Upon Sponsor Notification of Study Completion (ie, trial completion), sites will be instructed to bring subjects who remain on treatment for an EOT visit. An EOS visit will occur approximately 30 days later for subjects on treatment at Sponsor Notification of Study Completion.

Subjects who prematurely discontinue study drug are to complete the EOT visit within approximately 30 days, and will continue in the study for all subsequent study visits until study completion. If the next scheduled visit after EOT assessments is <30 days, subjects can skip that visit and return for the next subsequent visit (eg, if the EOT is 15 days prior to the scheduled Month 36 visit, they can skip Month 36, and come in at Month 40). All procedures and assessments should be performed at subsequent visits until EOS except where footnoted in assessment column. Upon Sponsor Notification of Study Completion, subjects who prematurely discontinued study medication ≥30 days before will return for an EOS visit. Subjects who are still being followed in the study but who discontinued study medication within 30 days of Sponsor Notification of Study Completion will return for an EOS visit approximately 30 days after their last dose of study medication.

ACR = albumin-to-creatinine ratio; AE = adverse event, ECG = electrocardiogram, EOS = end of study; EOT = end of treatment; F/U = Follow-up; HbA_{1c} = glycosylated hemoglobin, hsCRP = high sensitivity C-reactive protein; incl. = including; IxRS = interactive voice and/or web response system; MACE = major adverse cardiovascular events; MACE+ = MACE or hospitalization for unstable angina or heart failure, and any coronary revascularization; PGx = pharmacogenomics, Unsch = unscheduled.

- a. Visit 2 = Baseline/Randomization. The first dose should be taken at this visit. (revised per Amendment 01)
- b. Assessments are only to be performed if clinically indicated or necessary due to state controlled substance requirements. (revised per Amendment 01)
- c. Window ±10 days for all visits after Visit 2, other than the EOS visit which has a window of +10 days. Month is shown unless otherwise indicated; 1 month = approximately 30 days.
- d. Only for a subset of subjects at selected sites. Baseline echocardiograms will be performed in between Visits 1 and 2, after the results of screening assessments have been obtained but prior to randomization, and subject eligibility is confirmed. ECHOs will be performed until at least 1000 subjects have completed the Month 36 echocardiographic assessment. (revised per Amendment 02)

Table 4 Schedule of Procedures/Assessments in Study APD356-G000-401

Phase	Pre-randomization	Randomization																		
Period	Screening	Treatment																	F/U	
Visit	1	2 ^a	3	4	5	6	7	8	9	10	11	12	13	14	15	16	17	EOT	EOS	Unsch ^b
Month ^c	Days -30 to -1	Day 1	3	6	9	12	15	18	21	24	28	32	36	40	44	48	52	56		
Assessment (revised per Amendment 01)																				

- e. For subjects who discontinue study drug early, these assessments will be stopped after the EOT visit.
- f. Renal function parameters and glycemic profile should be obtained at all specified visits, regardless of study drug status. (revised per Amendment 01)
- g. Serum cystatin C will be measured at Baseline and yearly thereafter in the subpopulation with CKD Stage 1 or 2 at Baseline. Serum creatinine will be measured in chemistry blood samples if chemistry assessments are performed.
- h. Serum pregnancy tests will be conducted at Screening. A urine pregnancy test will be conducted at randomization.
- i. These assessments should be done if a telephone contact is performed in lieu of a clinic visit.

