The study will consist of 2 phases: Prerandomization and Randomization. The Prerandomization Phase will last up to 30 days and consist of 1 visit during which subjects will be screened for eligibility. The Randomization Phase will consist of 2 periods: Treatment and Follow-up. The Treatment Period will last for approximately 5 years with approximately 18 visits. The first dose should be taken at Visit 2. (revised per Amendment 01) The Follow-up Period extends from the end of treatment (EOT) visit to the EOS visit. Sponsor Notification of Study Completion will occur once 1401 MACE+ events, 460 MACE events, and median treatment duration of 2.5 years have accrued. This is expected to occur on or before October 2018. Following this announcement (“Sponsor Notification of Study Completion”), sites will be instructed to bring subjects who remain on treatment for an EOT visit. An EOS visit will occur approximately 30 days later for subjects on treatment at Sponsor Notification of Study Completion. (revised per Amendment 01) Subjects who are still being followed in the study but have already discontinued study medication ≥ 30 days before will return for an EOS visit. Subjects who are still being followed in the study but who discontinued study medication within the last 30 days will return for an EOS visit approximately 30 days after their last dose of study medication.

Subjects will receive lorcaserin HCl 10 mg BID or placebo BID for approximately 5 years. Throughout the duration of the study, subjects will be provided with instructions regarding a reduced-calorie diet and increased physical activity program (see Appendix 4). Echocardiography will be performed on a subset of subjects at Baseline and at 6, 12, 18, and 24 months, and yearly thereafter. Acquisition of new ECHO data in all subjects will cease when

at least 1000 subjects have completed the Month 36 echocardiographic assessment. (revised per Amendment 02)

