- Time from randomization to first occurrence of 2 consecutive assessments within the same component of the composite endpoint or time to first occurrence of renal transplant or renal death, on scheduled or nonscheduled visits at least 30 days apart, indicative of new onset renal impairment or worsening of existing renal impairment (first occurrence of any of the following events: microalbuminuria, macroalbuminuria, worsening

albuminuria, newly developed CKD or worsening of CKD, or doubling of serum creatinine, as defined above, or any of the following: ESRD, renal transplant, renal death) in all subjects. (revised per Amendment 02)

- Time from randomization to first occurrence of 2 consecutive assessments within the same component of the composite endpoint or time to first occurrence of renal transplant or renal death, on scheduled or nonscheduled visits at least 30 days apart, indicative of new onset renal impairment or worsening of existing renal impairment (first occurrence of any of the following events: microalbuminuria, macroalbuminuria, worsening albuminuria, newly developed CKD or worsening of CKD, or doubling of serum creatinine, as defined above, or any of the following: ESRD, renal transplant, renal death) in subjects with prediabetes at Baseline (revised per Amendments 01 and 02)
- Time from randomization to first occurrence of 2 consecutive assessments within the same component of the composite endpoint or time to first occurrence of renal transplant or renal death, on scheduled or nonscheduled visits at least 30 days apart, indicative of new onset renal impairment or worsening of existing renal impairment (first occurrence of any of the following events: microalbuminuria, macroalbuminuria, worsening albuminuria, newly developed CKD or worsening of CKD, or doubling of serum creatinine, as defined above, or any of the following: ESRD, renal transplant, renal death) in subjects with T2DM at Baseline (revised per Amendment 02)
- Time from randomization to first occurrence of 2 consecutive assessments, on scheduled or nonscheduled visits at least 30 days apart, indicative of improvement in renal function (first occurrence of regression of albuminuria or regression of CKD) in subjects with T2DM at Baseline

Secondary Safety Endpoints Assessing Cardiac Valve Function and Pulmonary Arterial Pressure: (revised per Amendment 02)

- Proportion of subjects without FDA-defined valvulopathy at Baseline who develop FDA-defined valvulopathy at 1 year

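### The Table 4 skip rule lets a subject with an early EOT visit miss a scheduled safety echocardiogram, because echo is the one clinical measurement that the EOT column does not repeat

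*Protocol*

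**What the plan says.** The Notes to Table 4 (Protocol 9.5.2.1) ask a subject who stops study drug early to complete an EOT visit within about 30 days and then to stay on the visit schedule. They allow one relaxation: "If the next scheduled visit after EOT assessments is <30 days, subjects can skip that visit and return for the next subsequent visit". The illustration given is: "if the EOT is 15 days prior to the scheduled Month 36 visit, they can skip Month 36, and come in at Month 40".

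Off-drug follow-up is otherwise complete: "All procedures and assessments should be performed at subsequent visits until EOS except where footnoted in assessment column". The footnote that ends an assessment is e: "For subjects who discontinue study drug early, these assessments will be stopped after the EOT visit". The echo row is labelled "Echocardiogram ^d". It carries footnote d (substudy sites, timing of the baseline echo, and the stopping rule for echo acquisition) and not e, so echo continues after drug is stopped. The row is marked at Screening and Months 6, 12, 18, 24, 36 and 48. It is blank at EOT, EOS and Unscheduled. Protocol 9.1 agrees: "Echocardiography will be performed on a subset of subjects at Baseline and at 6, 12, 18, and 24 months, and yearly thereafter".

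The Month 12 echo feeds a secondary safety endpoint in Protocol 9.7.1.1: "Proportion of subjects without FDA-defined valvulopathy at Baseline who develop FDA-defined valvulopathy at 1 year". The change in pulmonary artery systolic pressure at 1 year is also a secondary safety endpoint. Echo results at 2 years and later are exploratory.

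**The concern.** A skip is harmless if the EOT visit, held less than 30 days earlier, has already collected what the skipped visit would have collected. For laboratory tests, ECG, weight and waist circumference it has. For echo it has not, and nothing in either document moves the echo to EOT, to the next visit or to a make-up visit.

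The subjects affected have recently come off drug, some of them because of an adverse event. Images missing for this reason are missing in connection with discontinuation, in a substudy that Protocol 9.5.3 says was required by the FDA. The SAP offers no remedy. The 1-year valvulopathy analysis (SAP 5.4.3) is a logistic regression with no stated handling of a missing echo, SAP 5.3.5 deals with MACE/MACE+ and vital status, and SAP 8.6 covers two or more echoes in a window but not an empty one.

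**Working it through.** The plan states no figure on this point, so there is nothing to reproduce. The check has five parts.

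**1. What the EOT column leaves out.** Each visit from Month 3 to Month 52 in Table 4 was compared with the EOT column. At every visit, diet and exercise counselling is not repeated at EOT. At Months 6, 12, 18, 24, 36 and 48, echo is not repeated either. No other scheduled clinical measurement is lost.

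**2. Time between echoes after a skip** (months, from the Table 4 echo row).

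| Visit skipped | Previous echo | Next scheduled echo | Gap |
|---|---|---|---|
| 6 | Baseline | 12 | 12 |
| 12 | 6 | 18 | 12 |
| 18 | 12 | 24 | 12 |
| 24 | 18 | 36 | 18 |
| 36 | 24 | 48 | 24 |
| 48 | 36 | none | no later echo |

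The planned spacing is 6 months up to Month 24 and 12 months after that. In the protocol's example the subject returns at Month 40, which has no echo. Month 48 may not take place either, because acquisition stops for everyone once at least 1000 subjects have had the Month 36 echo. Once that rule is met, a skip loses nothing further.

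**3. Whether the 1-year slot is empty** (SAP Table 8). The scheduled echo days are 180 (Month 6) and 540 (Month 18).
- 6-month column, Month 12 = days 271-450: neither echo falls inside, so the slot is empty.
- Yearly column, Month 12 = days 2-540: the Month 6 echo falls inside, and so does a Month 18 echo done by day 540. The slot can be filled.

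SAP 8.6 does not assign echo to a column. Neither column matches the full echo schedule: the 6-month column ends at Month 24, and the yearly column has no Month 6 or Month 18 slot.

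**4. How many subjects could skip the Month 12 echo.** Inputs: about 3600 echo subjects (Protocol 9.5.1.5) and a 30-day exposure band (Table 4 Notes). Assumptions, because the documents give no rate: a fraction p stops drug in year 1, with EOT dates spread evenly over 360 days.

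Number eligible = 3600 × p × 30/360
- p = 5%: 15 (0.4%)
- p = 10%: 30 (0.8%)
- p = 20%: 60 (1.7%)
- p = 30%: 90 (2.5%)

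Over the whole schedule, if early EOT dates are uniform over 1680 days, 6 × 30/1680 = 10.7% of them fall within 30 days before an echo visit.

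**5. Where an echo done at EOT would be counted.** For Month 12, an EOT visit in the 30 days before day 360 falls on about days 330-360, inside both 271-450 and 2-540. For Month 36 (day 1080) it falls on about days 1050-1080, inside the yearly window of 901-1260. SAP Table 8 therefore already places such an echo in the intended visit.

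**The case against.** The strongest reply is that the consequence is small and partly covered.

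- **The 1-year endpoint.** A reader might infer that a skipped Month 12 echo removes the subject from the 1-year valvulopathy analysis. The documents do not establish this, because it depends on a window column that the SAP leaves open. What stands is that the slot is empty under one reading. Under the other it may be filled by an image taken about six months before or after the intended time.
- **Other endpoints.** The 1-year pulmonary pressure analysis is a repeated-measures model, so a subject without a Month 12 echo still contributes other visits. No named endpoint is read at Month 6 or Month 18, and losses at Months 24 and 36 touch exploratory endpoints only. It would be wrong to treat every echo visit as an equal loss.
- **The count.** The rule is permissive, and a site may still do the scheduled echo. Protocol 9.5.5.1 ties the early EOT visit to permanent discontinuation and encourages restart. The 30-60 subjects are therefore an upper bound at the assumed rates, not an expected number.
- **Other routes to a missing echo.** Subjects off drug may have visits by telephone, with only an attempt at one in-person visit a year, and no echo is done by telephone. The documents do not show that the skip rule is the main cause of missing echoes.
- **Standing of the endpoint.** Valvulopathy at 1 year is outside the gatekeeping hierarchy, and its analysis is repeated with three earlier studies pooled.

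All of this limits the size of the problem. None of it restores the echo that the note allows to be skipped.

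**Conclusion.** The point holds as an internal mismatch. The protocol intends echo to continue off drug, yet its skip rule and its own example allow a scheduled echo to go undone, and the EOT visit does not supply it. That the EOT visit is meant to stand in for the skipped visit is an inference from the near-complete EOT column, since the Notes give no reason.

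The likely effect is small: at most about 30-60 of 3600 subjects (0.8-1.7%) for the 1-year echo if 10-20% stop drug evenly through year 1, and 15-90 (0.4-2.5%) if 5-30% do. A reader might go further and infer a material bias in the valve-safety comparison. The documents do not support that. They give no discontinuation rate by arm, and among those who stop, the loss depends on where the EOT date falls relative to an echo visit. The case for acting is that the missing images are linked to stopping drug in a required safety substudy, and that the gap costs little to close.

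**What to change.** Amend the Table 4 note so that echo-substudy subjects do not skip a visit with a scheduled echo unless that echo is done at the EOT visit. Add a conditional, footnoted mark for echo in the EOT column to match. State in SAP 8.6 which window column of Table 8 governs echo. No rule is needed to reassign an EOT echo, because it already falls in the window of the visit it replaces.

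The cost is one sentence, one footnoted mark and one line in the SAP. No echo is added beyond those already scheduled. The downside is that a few subjects attend a visit, or have the echo at EOT, that they could otherwise have skipped. Echoes lost through telephone visits are not addressed by this change.

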During this study, the endpoints of MACE and MACE+ will need to be reported in an expedited fashion by investigators to the CEC and to the Eisai Product Safety Department, but will not be

recorded as SAEs in the clinical trial database or be required to be reported to regulatory authorities in an expedited timeframe, with the exception of MACE or MACE+ events that are considered by the investigator to be at least possibly related to the study drug (ie, where there is evidence to suggest a causal relationship). (revised per Amendment 01)

All MACE and MACE+ events are to be reported on the AE CRF and the MACE/MACE+ section of the CRF, but will not be considered as AEs.

The following hospitalizations are not considered to be SAEs because there is no “AE” (ie, there is no untoward medical occurrence) associated with the hospitalization:

- Planned hospitalizations required by the protocol
- Hospitalization planned before informed consent (where the condition requiring the hospitalization has not changed post study drug administration)
- (revised per Amendment 01)
- Hospitalization for routine maintenance of a device (eg, battery replacement) that was in place before study entry

LABORATORY MEASUREMENTS

Clinical laboratory tests to be performed, including hematology, chemistry, and urinalysis, are summarized in [Table 3](#). Subjects should be in a seated or supine position during blood collection. The Schedule of Procedures/Assessments ([Table 4](#)) shows the visits and timepoints at which blood for clinical laboratory tests and urine for urinalysis will be collected in the study.

Table 3 Clinical Laboratory Tests

Category	Parameters
Hematology	hematocrit, hemoglobin, platelets, RBC count, and WBC count with differential (bands, basophils, eosinophils, lymphocytes, monocytes, neutrophils)
Chemistry	
Electrolytes	bicarbonate, chloride, potassium, sodium
Liver function tests	ALT, alkaline phosphatase, AST, direct bilirubin, total bilirubin, GGT
Renal function parameters	blood urea/blood urea nitrogen, creatinine
Other	albumin, calcium, globulin, glucose, lactate dehydrogenase, LDL-C, HDL-C, phosphorus, total cholesterol, total protein, triglycerides, uric acid,
Urinalysis	glucose, ketones, protein, RBCs, WBCs, albumin and creatinine for ACR
Other	HbA _{1c} , serum cystatin C, fasting insulin, FPG, hsCRP, fibrinogen, serum pregnancy, urine drug screen

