#### 5.8 EXPLORATORY ENDPOINT ANALYSES

• The change from Baseline in CV risk factors (body weight, BMI, waist and hip circumference, dyslipidemia, insulin level, hypertension, inflammatory biomarkers) will be analyzed using a mixed-effects model with repeated measures with treatment, month, month by treatment interaction and stratification variable (presence of established CV disease or CV risk factors without established CV disease) as factors and Baseline value as a covariate. Comparison between lorcaserin HCl and placebo will be made at 1year. The estimated treatment difference in the LSM between lorcaserin HCl and placebo, p-value, and the two-sided 95% CI will be calculated. The ITT will be used for this analysis. SAS PROC MIXED will be used using an unstructured covariance matrix (TYPE=UN). If the model fails to converge then other covariance structures such as; Heterogeneous Toeplitz covariance structure (TYPE= TOEPH), heterogeneous Autoregressive (TYPE=ARH(1)) or compound symmetry (TYP=CS) will be used.

- For subjects with NAFLD at Baseline, the change from Baseline in liver function tests (AST, ALT, alkaline phosphatase, GGT, total and direct bilirubin) will be analyzed using a mixed-effects model with repeated measures with treatment, month, month by treatment interaction and stratification variable (presence of established CV disease or CV risk factors without established CV disease) as factors and Baseline value as a covariate. Comparison between lorcaserin HCl and placebo will be made at 1 year. The estimated treatment difference in the LSM between lorcaserin HCl and placebo, p-value, and the two-sided 95% CI will be calculated. The ITT will be used for this analysis. SAS PROC MIXED will be used using an unstructured covariance matrix (TYPE=UN). If the model fails to converge then a Heterogeneous Toeplitz covariance structure (TYPE= TOEPH) will be used.
- The proportion of subjects who meet FDA-defined valvulopathy in echocardiographically determined heart valve changes will be analyzed using a logistic GLMM for repeated measures including treatment, month, month by treatment interaction as factors and baseline BMI as a covariate. Comparison between lorcaserin HCl and placebo will be made at 2 years and yearly thereafter. The odds ratio, p-value and 2-sided 95% CI will be calculated. The FDA-defined Valvulopathy Analysis Set will be used for this analysis.

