#### **8.6 DEFINITION OF VISIT WINDOWS**

Table 4 of the protocol presents the schedule of procedures/Assessments. Some procedures/assessments are performed at 3 months, 6 months or yearly intervals. Table 8 presents the protocol specified visits/months and corresponding time windows used for visit-wise analyses are presented in terms of days relative to the first dose. For subjects that are randomized, the last available assessment on or before the randomization date will be used as the Baseline-Day 1. If more than one measurement is included in a visit window, the measurement collected closest to the scheduled date will be used in the analysis. In the case where two measurements were collected an equal number of days before and after the Scheduled Day the later of the two measurements will be used for analysis.

For ECHO and PAH assessments when assessing a new or worsened event then the most severe assessment will be selected if 2 or more assessments fall within a visit window.

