**Table 8 Visit Windows Measurements** 

Scheduled Visit	Scheduled Month	Scheduled Day	Time Window (Days)		(Days Mo Inte	Vindow ) For 6 onth erval sments	Time W (Days Yea Inte Assess	) For arly rval
1	Screening		-30	-1				
2	Baseline/ Randomization	1	1		1		1	
3	3	90	2	135				
4	6	180	136	225	2	270		
5	9	270	226	315				
6	12	360	316	405	271	450	2	540
7	15	450	406	495				
8	18	540	496	585	451	630		
9	21	630	586	675				
10	24	720	676	780	631	810	541	900
11	28	840	781	900				
12	32	960	901	1020				
13	36	1080	1021	1140			901	1260
14	40	1200	1141	1260				
15	44	1320	1261	1380				
16	48	1440	1381	1500			1261	1620
17	52	1560	1501	1620				
EOT	56	1680	1621	1710				
EOS	58	1740	1711	Open				

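### SAP Table 8 opens the first 6-month and yearly windows on day 2, so a premature end-of-treatment sample from the first weeks can stand as an observed Month 6 or Month 12 value in exploratory analyses

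*Protocol*

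**What the plan says.** SAP section 8.6 places each result at a visit by counting days from first dose, using Table 8 ("Visit Windows Measurements"). When a window holds more than one result, "the measurement collected closest to the scheduled date will be used in the analysis". Table 8 has three sets of windows: a standard column, one for 6-monthly assessments and one for yearly assessments. The first window in each is:

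- Standard, Month 3: days 2–135.
- 6-month column, Month 6: days 2–270.
- Yearly column, Month 12: days 2–540.

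The table's EOT row covers only days 1621–1710. No test is tied to a column by name, and no rule covers an EOT sample taken early.

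Protocol Table 4 takes waist/hip, hsCRP, fibrinogen and ACR yearly after baseline and at EOT. FPG and insulin are taken at Months 6 and 12, yearly thereafter and at EOT, with no Month 3 draw. Chemistry is drawn at Months 6, 12, 24, 36 and 48, at EOT and at EOS. Protocol section 9.5.1.5, Table 3, puts liver tests ("ALT, alkaline phosphatase, AST, direct bilirubin, total bilirubin, GGT") and lipids (within "LDL-C, HDL-C, phosphorus, total cholesterol, total protein, triglycerides, uric acid") in the chemistry panel.

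The chemistry row carries footnotes e and f. Footnote e reads "For subjects who discontinue study drug early, these assessments will be stopped after the EOT visit". Footnote f keeps part of the testing going: "Renal function parameters and glycemic profile should be obtained at all specified visits, regardless of study drug status". Lipids and liver tests are not in that exemption. A subject who stops drug is asked to attend EOT within about 30 days and then stays in follow-up.

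SAP section 5.8 compares cardiovascular risk factors, liver tests (in subjects with NAFLD) and ACR at 1 year with repeated-measures models, stating "The ITT will be used for this analysis". FPG, insulin and HOMA-IR at 6 months are analysed by ANCOVA in subgroups with T2DM.

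**The concern.** The closest-value rule only chooses among results in the same window. A result that is alone in its window is kept, however far it lies from the target day. A subject who stops drug in the first weeks gives a full set of EOT samples soon afterwards. If nothing later falls in the first window, that sample enters the analysis as an observed Month 6 or Month 12 value.

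Such a value reflects a few weeks of exposure, not six or twelve months. The repeated-measures model would treat it as real data at that visit instead of as missing. The treatment difference would then mix short and full exposure, to a degree that depends on how many subjects in each arm stop early.

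**Working it through.** **Inputs.** Scheduled days and windows come from SAP Table 8, and test schedules and footnotes from Protocol Table 4.

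**Step 1: reproduce the table's boundaries.** The rule is (scheduled day + next scheduled day) / 2.

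- 6-month column: (180+360)/2 = 270; (360+540)/2 = 450; (540+720)/2 = 630; (720+900)/2 = 810.
- Yearly column: (360+720)/2 = 540; (720+1080)/2 = 900; (1080+1440)/2 = 1260; (1440+1800)/2 = 1620.
- Standard column: (90+180)/2 = 135, and so on to (1680+1740)/2 = 1710.

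All agree with Table 8, taking days 900 and 1800 as the next step after the last visit in the 6-month and yearly columns. Only the lower limit of each first window, day 2, departs from the rule.

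**Step 2: apply the rule to those lower limits,** with day 1 as the preceding scheduled day.

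- Month 6: (1+180)/2 = 90.5, so the window would open on day 91.
- Month 12, yearly column: (1+360)/2 = 180.5, so it would open on day 181.

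**Step 3: width of the windows.** The yearly Month 12 window is 540−2+1 = 539 days wide, reaching 360−2 = 358 days before target and 540−360 = 180 after. Opened at day 181 it would reach 179 before and 180 after. The 6-month Month 6 window reaches 180−2 = 178 days before target and 270−180 = 90 after. Opened at day 91 it would reach 89 before and 90 after.

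**Step 4: where an EOT sample lands under Table 8 as written.**

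| Sample day | Standard | 6-month | Yearly |
|---|---|---|---|
| 7, 14, 21, 30, 45, 60 or 90 | Month 3 | Month 6 | Month 12 |
| 180 | Month 6 | Month 6 | Month 12 |
| 270 | Month 9 | Month 6 | Month 12 |
| 271 | Month 9 | Month 12 | Month 12 |
| 360 | Month 12 | Month 12 | Month 12 |

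As an example, drug stopped on day 30 with EOT on day 45 gives a sample 360−45 = 315 days early for Month 12 (yearly column), or 180−45 = 135 days early for Month 6 (6-month column).

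**Step 5: match tests to columns.**

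- Waist/hip, hsCRP, fibrinogen and ACR have only yearly draws besides EOT and EOS, so the yearly column fits them. They continue after drug is stopped. The early EOT value is used only if no result nearer day 360 falls in the window.
- FPG and insulin, and hence HOMA-IR, have their first post-baseline draw at Month 6. Under the 6-month column an early EOT sample becomes the Month 6 value if the Month 6 visit is missed.
- Lipids and liver tests end at a premature EOT, so there is no later result to displace the early one unless drug is restarted. Under the yearly column it is the Month 12 value. Under the 6-month column it is a Month 6 value that informs Month 12 through the model. Chemistry fits neither column cleanly: the yearly column merges its Month 6 and Month 12 draws, and the 6-month column ends at Month 24.

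**The case against.** The strongest reply is that the SAP never applies the yearly column to chemistry. The panel has a Month 6 draw, so the 6-month column is the natural choice for the first year, and there Month 12 is days 271–450, out of reach of a sample from the first weeks. This stands. A reader might infer that the plan makes early lipid and liver results the 1-year values. The documents leave that open, and the 6-month window by itself can produce only a Month 6 value. SAP section 9 also places derivation rules in separate documents, which may settle the column.

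For the other measures, attendance at the scheduled visit removes the problem through the closest-value rule, and Protocol section 9.5.5.1 encourages restarting drug. Both points stand and limit how often the case arises. Still, Protocol section 9.5.5.1 lets a telephone visit replace a clinic visit, so missed samples are foreseeable.

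Two further inferences are tempting but unsupported. One is that the intent-to-treat label is breached: SAP section 5.2.1 defines that set as all randomised subjects and does not promise sampling after drug is stopped. The other is that footnote e is an error to be removed: the protocol's revision history records it as following an FDA recommendation.

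None of this explains why the first windows open on day 2 when every other boundary follows the midpoint rule.

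**Conclusion.** The point holds as a defect in the lower bounds of Table 8. Followed as written, the table can label a sample from the first weeks as an observed Month 12 value for yearly measures, or as a Month 6 value for FPG, insulin and HOMA-IR, when the scheduled visit is missed. For lipids and liver tests the early value enters at Month 12 or at Month 6, depending on a column choice the SAP does not state. The match of tests to columns is inferred from the visit schedule.

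The number of subjects affected cannot be computed. The documents give no early drug-discontinuation rate, and the 5% annual drop-out is a sample-size assumption. For scale only, each 1% of 12,000 subjects is 120; an assumed 1% to 10% stopping drug this early would be 120 to 1,200 subjects. For measures that continue off drug, only those who also miss the scheduled visit count. The liver-test analysis covers only subjects with NAFLD, and the 6-month analyses only subgroups with T2DM.

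The endpoints concerned are exploratory. MACE, MACE+ and conversion to T2DM are time-to-event endpoints and do not depend on these windows. This is a minor point with a cheap remedy.

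**What to change.** In SAP Table 8 and section 8.6:

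1. Apply the table's own midpoint rule to the lower bounds: open Month 6 (6-month column) at day 91 and Month 12 (yearly column) at day 181. Leave the later windows unchanged.
2. Assign chemistry (lipids and liver tests) to windows in which Month 6 and Month 12 stay separate, and name the bounds that serve Months 36 and 48, since the 6-month column stops at Month 24.
3. State that premature-EOT samples taken before the opening day are not assigned to Month 6 or Month 12. The repeated-measures models then treat those visits as missing.

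The cost is a SAP edit and slightly fewer values at Month 6 and Month 12. In the 6-month ANCOVA, which uses a single time point, a subject without an assigned value would drop out, because the SAP states no imputation for that analysis. No protocol change, visit or extra sample is needed, and footnote e can stay as it is.
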